Brief Outline of Treatment Plan: Patients will be randomized on day 4 of induction therapy to either conventional or intensive blood pressure goals. Patients will be treated with the long-acting antihypertensive lisinopril to achieve blood pressure control as indicated by their randomized arm. Long-acting therapy will be adjusted every 3-4 days as needed to achieve targeted control based on the median of blood pressures obtained in that period. Treatment of hypertension to the target will continue until the completion of reinduction II therapy. Patients will be evaluated for osteonecrosis as indicated in their primary therapeutic protocol using MRI during reinduction II.
Study Design: Randomized unblinded trial of conventional vs. intensive hypertensive control. Evaluation of the MRIs defining the primary endpoint will be performed by a blinded radiologist.
Sample Size: We will randomize 160 evaluable patients (180 total).
Data Management: Data management and statistical analysis will be provided locally by the Comprehensive Cancer Center Hematological Malignancies Program and the Biostatistics Department at St. Jude Children’s Research Hospital.
Human Subjects: The risks to subject will be related to the toxicity of antihypertensive therapy. Side effects are anticipated to be mild and limited to reversible orthostatic/postural hypotension and transient increases in creatinine. Patients will be informed of this and other minor side effects during informed consent discussion. Adverse events will be monitored and reported and treated appropriately.

TABLE OF CONTENTS

1.0	OBJECTIVES	1
1.1	Primary Objective	1
1.2	Secondary Objectives	1
1.3	Exploratory Objectives	1
2.0	BACKGROUND AND RATIONALE	2
2.1	Background	2
2.2	Rationale	2
2.3	Background and Rationale for Ancillary and Exploratory Studies	3
3.0	RESEARCH PARTICIPANT ELIGIBILITY CRITERIA AND ENROLLMENT	4
3.1	Inclusion Criteria	4
3.2	Exclusion Criteria	4
3.3	Research Participant Recruitment and Screening	5
3.4	Enrollment on Study at St. Jude	5
3.5	Enrollment Instructions for Collaborating Sites	5
4.0	TREATMENT PLAN	6
4.1	Treatment	6
4.2	Participation of St. Jude Affiliates in the Treatment Plan	9
4.3	Treatment Modifications for Collaborating Sites	9
4.4	Supportive Care	9
4.5	Symptom Survey and Semi-structured Interviews	10
5.0	REQUIRED EVALUATIONS, TESTS, AND OBSERVATIONS	12
5.1	Pre-Study Evaluations	12
5.2	Evaluations during Therapy	12
5.3	Response Evaluations	13
5.4	Off-Study Evaluations	13

APPENDIX I: Performance Status Criteria

1.0 OBJECTIVES

1.1 Primary Objective

- 1.1.1 Compare the frequency of radiographically extensive osteonecrosis in patients receiving intensive compared to conventional antihypertensive therapy.

1.2 Secondary Objectives

- 1.2.1 Evaluate the efficacy of intensive antihypertensive control compared to conventional antihypertensive control in the prevention of clinically significant (CTCAE Grade 2 or higher) and radiologically extensive osteonecrosis, overall and stratified by joints.
- 1.2.2 Compare the frequency of clinically significant and radiographically extensive osteonecrosis in patients receiving antihypertensive therapy and historical controls.
- 1.2.3 Compare blood pressures achieved in intensive and conventional arms using both pressures obtained as part of routine patient care and ambulatory blood pressure monitoring.
- 1.2.4 Compare levels of vascular dysfunction as measured physiologically, radiographically, and in blood samples in patients receiving intensive compared to standard antihypertensive therapy.

1.3 Exploratory Objectives

- 1.3.1 Identify predictive patterns of blood biomarkers which identify patients at high-risk of developing clinically significant osteonecrosis.
- 1.3.2 Identify MRI findings during late induction which correlate with osteonecrosis lesions seen during reinduction.
- 1.3.3 Identify patterns of diurnal blood pressure variation as measured by ambulatory blood pressure monitoring associated with the later development of osteonecrosis.
- 1.3.4 Compare induction blood pressure control and intervention arm to echocardiographic changes at reinduction II.
- 1.3.5 Evaluate patient-reported, health-related quality of life in patients during induction and after 1.5 years of therapy when many experience the symptoms of osteonecrosis.

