2.2 Rationale

Based on the retrospective clinical and prospective preclinical data, undertreatment of hypertension is associated with an approximately 2-fold increased risk of developing osteonecrosis after accounting for other known risk factors. Data from both adult^{14,15} and pediatric¹⁶ populations shows a benefit to more intensive blood pressure control compared to conventional control. Due to the risks of complications from untreated hypertension (e.g. posterior reversible encephalopathy syndrome), it is both impractical and unethical to randomize patients to no treatment for their hypertension. We will therefore test the efficacy of intensive hypertensive control (targeted to the 50-75th

percentile for age, sex, and height, systolic) compared to conventional antihypertensive control (targeted to the 90-95th percentile for age, sex, and height, systolic). We have chosen slightly higher systolic blood pressure goals for the intensive arm compared to the ESCAPE trial¹⁶ due to the presence of anemia and risk for infection in pediatric ALL patients, both of which may predispose to an increased risk of symptomatic hypotension.

The Children's Oncology Group AALL0232 and CCG1961 trials demonstrated differences in osteonecrosis in patients receiving dexamethasone instead of prednisone during induction, or continuous instead of alternate week dexamethasone during delayed intensification, respectively.^{2,5} These data support the critical role that these two steroid-intensive phases of therapy (termed induction and reinduction in St. Jude Total Therapy protocols) play in the development of osteonecrosis. The planned intervention will therefore encompass these two periods.

Although TOT17 includes an optional randomization for vincristine and dexamethasone duration (49 weeks vs. 101 weeks), the primary endpoint in this study (Reinduction II MRI) occurs prior to that randomization. Thus, the randomization will not impact the primary outcome of the study. Furthermore, review of symptomatic osteonecrosis timing on TOTXVI suggests that the majority of patients develop symptoms prior to this timepoint. For secondary endpoints including CTCAE symptomatic osteonecrosis, we will consider dexamethasone duration as a covariate.

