10.2 Randomization

Open-label, stratified block randomization with block size of 4³⁹. Randomization will be stratified by site (SJCRH and other), gender, self-declared race/ancestry (White Non-Hispanic and other) and hypertension requiring >1 dose of medication before Day 4 (Yes/No).

Analyses for the primary and secondary objectives will not be stratified. If it is determined that certain important factors are not balanced between the two treatment arms, appropriate regression models (such as logistic or integer response models) will be applied. The power assessment below is based on an unstratified Chi-square test.

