10.5 Secondary Objectives

Evaluate the efficacy of intensive antihypertensive control compared to conventional antihypertensive control in the prevention of clinically significant (CTCAE Grade 2 or higher) and radiologically extensive osteonecrosis, overall and stratified by joints.

A one-sided Chi-square test will be performed on a 2x2 contingency table similar to that in the primary objective, only now the columns are CTCAE Grade 2 ON (No/Yes). This analysis will also be performed for the knees and hips separately. MRI-defined extensive osteonecrosis will also be performed as described above, for knees and hip separately using Chi-square test on contingency tables.

Compare the frequency of clinically and radiographically significant osteonecrosis between patients receiving antihypertensive intervention and historical controls.

The historical control cohort consists of all patients enrolled on TOT-XV and TOT-XVI studies with age at diagnosis 10 years or older. The rate of clinically significant (CTCAE Grade 2+) ON and radiographically significant findings (number of affected joints) will be compared between the intensive BP treatment arm and the historical cohort by Chi-square tests.

Compare blood pressures achieved in intensive and conventional arms using both pressures obtained as part of routine patient care and ambulatory blood pressure monitoring.

The comparison will be done by regression modeling using mixed effect models to account for intra-patient repeated blood pressure measurements. The response variable is blood pressure, the explanatory variables include the BP control arm (intensive vs. conventional), age, sex, race and a random effect with AR(1) working covariance structure.

Compare levels of vascular dysfunction as measured physiologically, radiographically, and in blood samples in patients receiving intensive compared to standard antihypertensive therapy.

The levels of vascular dysfunction are measured by markers such as MRI, eNO synthetase, Von Willebrand Factor, TNF-alpha, D-dimer, PAI-1, E-selectin and ICAM-1; the measurements are all continuous. Each marker will be compared between the intensive BP treatment arm and the standard care arm by Wilcoxon rank-sum test.

Time frame: The analysis will begin within 6 months after the MRI assessments of the last randomized patient is completed.

Responsible investigators: [name], [name]

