10.6 Exploratory Objectives

Identify predictive patterns of blood biomarkers which identify patients at high-risk of developing clinically significant osteonecrosis.

Associations between the blood biomarkers and CTCAE grade 2 or higher ON will be analyzed using mixed-effect logistic regression models.

Identify MRI findings during late induction which correlate with osteonecrosis lesions seen during reinduction.

The MRI finding during late induction is represented by a 3-level ordinal variable (none, small, large). The ON lesions seen during reinduction are represented by a binary variable (large, less than large). The association will be tested by the Chi-square test on a 3-by-2 contingency table with ordered rows.

Compare induction blood pressure control and intervention arm to echocardiographic changes at reinduction II.

Echocardiographic changes at reinduction II is measured by the LV strain which is a continuous variable. Comparison of the LV strain between the intensive BP treatment and standard care arms will be performed by Wilcoxon rank-sum test.

Evaluate patient-reported, health-related quality of life in patients during induction and after 1.5 years of therapy when many experience the symptoms of osteonecrosis.

Survey response scores will be summarized by descriptive statistics including mean, standard deviation, minimum, maximum, quartiles, range and inter-quartile range.

Time frame: The analysis will begin within 6 months after the MRI assessments of the last randomized patient is completed, except for the last exploratory objective for which the analysis will begin within 6 months after the last randomized patient is followed for 1.5 years after completion of chemotherapy.

Responsible investigators: [name], [name]

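### Section 10.6 gives the exploratory predictor analyses no term for randomised arm: the early-MRI test (1.3.2) has no place for one and the biomarker model (1.3.1) names none, so a marker that treatment shifts may appear associated with osteonecrosis

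*Combined protocol and SAP*

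**What the plan says.** All places are in the combined protocol and SAP.

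- **Section 1.3, objective 1.3.1.** The aim is: "Identify predictive patterns of blood biomarkers which identify patients at high-risk of developing clinically significant osteonecrosis".
- **Section 10.6, objective 1.3.1.** The whole analysis is one sentence: "Associations between the blood biomarkers and CTCAE grade 2 or higher ON will be analyzed using mixed-effect logistic regression models". No covariates are listed.
- **Section 10.6, objective 1.3.2.** Induction MRI is coded none, small or large, and the reinduction lesion is coded large or less than large. Then: "The association will be tested by the Chi-square test on a 3-by-2 contingency table with ordered rows".
- **Timing.** The Protocol Summary says: "Patients will be randomized on day 4 of induction therapy to either conventional or intensive blood pressure goals". Under Section 5.2, serum is drawn at day 22 and in week 17 of continuation, and the induction MRI is done on days 23–28. No predictor is a pre-randomisation value.
- **Arm and the markers.** Secondary objective 1.2.4 is: "Compare levels of vascular dysfunction as measured physiologically, radiographically, and in blood samples in patients receiving intensive compared to standard antihypertensive therapy".
- **Arm and osteonecrosis.** Section 10.4 anticipates at least one extensively affected joint in 38.5% of controls and 20% of the intensive arm.
- **Adjustment elsewhere.** Section 10.2 says: "Analyses for the primary and secondary objectives will not be stratified". Its regression fallback follows that sentence and applies to factors found unbalanced between arms. Section 10.5 names arm in the blood-pressure model: "the explanatory variables include the BP control arm (intensive vs. conventional), age, sex, race". For symptomatic osteonecrosis as a secondary endpoint, Section 2.2 says: "we will consider dexamethasone duration as a covariate".
- **Numbers.** Section 10.8 gives 160 participants for 1.3.1 and 80 for 1.3.2.

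**The concern.** If the intensive target changes a marker and also changes the risk of osteonecrosis, arm is a common cause of both. Taken over all patients together, the marker then carries information about allocation, and allocation carries information about outcome. An association can appear even when, among patients managed to the same target, the marker says nothing about who develops osteonecrosis.

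Objective 1.3.1 aims to identify high-risk patients. A marker that only tracks allocation would not do that once everyone is managed to one target. At stake is the list of candidate predictors carried into later work. No primary or secondary conclusion depends on it.

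**Working it through.** **1. The plan's own figures.** The control rate is 0.854 × (50/120) + 0.146 × 0.20 = 0.356 + 0.029 = 0.385. Enumerating two binomial arms of 80 at 0.385 and 0.20, the one-sided Fisher exact test at 5% has power 78.66%, against the stated 78.7%. The rates used below are therefore the plan's own.

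**2. Assumptions.** The documents give no marker shift, no significance level for the exploratory tests and no by-arm Grade 2+ rates. I assume:
- a two-sided 5% level;
- 38.5% v 20% for both outcomes. For 1.3.2 this takes a large lesion to mean the primary-endpoint threshold;
- one marker value per patient and an ordinary logistic model for 1.3.1, because the mixed model is not specified further;
- a marker with no relation to outcome within either arm.

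**3. Formula for the pooled test.** Allocation is 1:1, so arm has variance 1/4. Let arm shift the marker mean by D and the risk by Δ, and let V be the within-arm marker variance. The pooled covariance is DΔ/4, the pooled marker variance is V + D²/4, and the outcome variance is p̄(1 − p̄). The test statistic is then centred at

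λ = √N × (DΔ/4) / √[(V + D²/4) × p̄(1 − p̄)],

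and it rejects with probability Φ(−1.96 + λ) + Φ(−1.96 − λ).

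**4. Objective 1.3.1, N = 160, V = 1, arm left out.** At 38.5% v 20%, Δ = 0.185, p̄ = 0.2925 and p̄(1 − p̄) = 0.2069. For D = 0.5 SD, λ = 12.65 × 0.0231 / √(1.0625 × 0.2069) = 0.624, which gives 9.6%.

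| Shift (SD) | 38.5% v 20%, formula | 38.5% v 20%, simulation runs | 38.5% v 25.5%, formula |
|---|---|---|---|
| 0.3 | 6.7% | 6–7% | 5.8% |
| 0.5 | 9.6% | 9–10% | 7.1% |
| 0.8 | 15.9% | 15–16% | 10.0% |
| 1.0 | 21.0% | 20–22% | 12.3% |

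The last column illustrates a weaker arm effect, in which 70% of the intensive arm gets the anticipated benefit: 0.7 × 0.20 + 0.3 × 0.385 = 0.2555. The 70% is borrowed from the target-attainment rule in Section 10.3. With arm in the model, simulated rejection stayed at 4.6–5.3% at every shift at 38.5% v 20%. With equal risks (0.40 in both arms), the model without arm stayed at 4–5% whatever the shift.

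**5. Objective 1.3.2, N = 80.** I assume a control split of 50/30/20% over none, small and large, scored 0, 1, 2. A cumulative odds ratio of 0.5 moves the intensive arm to 66.7/22.2/11.1%. The means are 0.700 and 0.444, so D = 0.256, and the variances are 0.610 and 0.469, so V = 0.540. Then λ = 8.94 × (0.256 × 0.185/4) / √[(0.540 + 0.016) × 0.2069] = 0.31, which gives 6.1%.

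| Cumulative OR | Pooled, formula | Pooled, simulation | Stratified by arm, simulation |
|---|---|---|---|
| 0.5 | 6.1% | 6.2% | 5.0% |
| 0.33 | 7.6% | 8.0% | 5.2% |
| 0.2 | 9.6% | 10.4% | 4.6% |

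**The case against.** **Section 10.6 does not exclude arm from 1.3.1.** A reader might infer that it does, but the text is silent on covariates. The figure of 160 participants does not settle it, since a model with arm would use the same 160. The blood-pressure model shows that the plan can name arm when it lists covariates. This stands: for 1.3.1 the defect is an unspecified model, and only the 1.3.2 test leaves arm out as written.

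**A shifted marker need not look like a predictor.** A reader might infer that it will. Even at a 1.0 SD shift, roughly four trials in five would not declare it, and with no arm effect on osteonecrosis nothing is inflated. Objective 1.2.4 asks for a comparison and states no direction or size of shift. This also stands, so the right word is "may".

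**With several markers, the family error is mostly a different problem.** For seven null markers (assumed correlation 0.3), the chance of at least one false predictor is already about 25% with arm in the model. That part is multiplicity, and an arm term does not change it.

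**Masking of real predictors is possible but not shown.** It needs treatment to move a marker against the direction of its risk association. The documents give no reason to expect that as readily as the reverse.

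**The pooled association may be partly real.** Section 2.1 attributes the preclinical benefit to less arteriopathy. If a marker lies on the path from blood pressure to osteonecrosis, the pooled and arm-adjusted analyses answer different questions. This is the strongest objection. It supports showing both results, but it does not support leaving the choice unstated.

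**Conclusion.** The concern holds as a minor point of specification. The 1.3.2 test as written cannot account for arm, and the 1.3.1 model does not say whether it will. The predictors are all post-randomisation and, on the plan's own hypotheses, arm may act on both predictor and outcome. The fallback in Section 10.2 does not reach exploratory objectives and addresses a different problem.

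At the plan's rates, false positives rise from 5% to about 6–10% for 1.3.2 (cumulative OR 0.5 to 0.2) and to about 7–22% for 1.3.1 if arm is omitted (shift 0.3 to 1.0 SD). With the weaker arm effect, the 1.3.1 range is about 6–12%. These sizes rest on assumed shifts, an assumed MRI split, a two-sided 5% level and, for 1.3.1, MRI rates in place of Grade 2+ rates. The direction of the problem and its removal by an arm term do not depend on those choices, provided arm affects both marker and outcome. Severity is minor because the objectives are exploratory and no decision in the plan hangs on them.

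**What to change.** In Section 10.6:

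- **1.3.2:** replace the single pooled table with the same ordered-row test stratified by randomised arm (Cochran-Mantel-Haenszel), or with a logistic model that contains arm.
- **1.3.1:** state that randomised arm is a covariate in the mixed-effect logistic model.

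Keep both arms in each analysis. The pooled result may be shown alongside, labelled as including any between-arm association, so that a marker mediating the treatment effect is not lost from view.

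The cost is two sentences of SAP wording and one degree of freedom in each analysis. No new data are needed, and in the simulations the arm term left the false-positive rate at about 5% when arm did not shift the marker.

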2.0 BACKGROUND AND RATIONALE

2.1 Background

Advancements in the treatment of acute lymphoblastic leukemia (ALL) have pushed the cure rate to greater than 90%.¹ Intensifying glucocorticoid use (i.e. prednisone and dexamethasone) has been key in accomplishing these outcomes. However, glucocorticoid-induced osteonecrosis (ON) is one of the most common dose-limiting toxicities of ALL therapy in children.²⁻⁶ Symptomatic cases (defined as Common Terminology Criteria for Adverse Events (CTCAE) grade 2-4) often occur during the first two years of treatment, and may result in early discontinuation of glucocorticoids from treatment. Age is the most significant risk factor, with ALL patients greater than 10 years of age at higher risk of developing ON.^{2,3,5,6} The most common affected joints are the hip, knee, and shoulder.⁷⁻⁹ In both Total XV³ and Total XVI¹⁰, the rate of symptomatic osteonecrosis in children age 10 or older was ~40%.

Recent work has demonstrated that patients with ALL age 10 or older at diagnosis who develop hypertension during glucocorticoid containing phases of therapy were more likely to develop osteonecrosis. Among 235 children treated on Total XV and Total XVI, osteonecrosis occurred in 52% of the 94 who developed hypertension compared to 38% of those who were normotensive [p=0.037, odds ratio (OR) 1.75, 95% confidence interval (95% CI) 1.02-3.01].¹¹ The association was maintained in a multivariable analysis of all known factors associated with either hypertension or osteonecrosis (p=0.03, OR 1.88, 95% CI 1.1-3.22). When the analysis was restricted to osteonecrosis that developed during protocol therapy, 52% of patients with hypertension developed osteonecrosis compared to 34% of normotensive patients (p=0.006, OR 2.11, 95% CI 1.2-3.6). Hypertension was also associated with an increased frequency of extensive epiphyseal involvement ($\geq 30\%$ of the surface effected) of the hip and knee joints on screening MRIs; this is significant as this degree of involvement is associated with joint collapse and the need for surgical intervention.^{12,13}

In preclinical models, dexamethasone and asparaginase produced hypertension as in patients with ALL. The use of either an angiotensin enzyme inhibitor or hydralazine reduced the frequency of osteonecrosis (15% vs. 38% and 3% vs. 36%, p<0.01 for both) through reductions in osteonecrosis-inducing arteriopathy.¹¹ The same regimen did not impact the antileukemic efficacy of chemotherapy *in vitro* or *in vivo*.

2.2 Rationale

Based on the retrospective clinical and prospective preclinical data, undertreatment of hypertension is associated with an approximately 2-fold increased risk of developing osteonecrosis after accounting for other known risk factors. Data from both adult^{14,15} and pediatric¹⁶ populations shows a benefit to more intensive blood pressure control compared to conventional control. Due to the risks of complications from untreated hypertension (e.g. posterior reversible encephalopathy syndrome), it is both impractical and unethical to randomize patients to no treatment for their hypertension. We will therefore test the efficacy of intensive hypertensive control (targeted to the 50-75th

percentile for age, sex, and height, systolic) compared to conventional antihypertensive control (targeted to the 90-95th percentile for age, sex, and height, systolic). We have chosen slightly higher systolic blood pressure goals for the intensive arm compared to the ESCAPE trial¹⁶ due to the presence of anemia and risk for infection in pediatric ALL patients, both of which may predispose to an increased risk of symptomatic hypotension.

The Children's Oncology Group AALL0232 and CCG1961 trials demonstrated differences in osteonecrosis in patients receiving dexamethasone instead of prednisone during induction, or continuous instead of alternate week dexamethasone during delayed intensification, respectively.^{2,5} These data support the critical role that these two steroid-intensive phases of therapy (termed induction and reinduction in St. Jude Total Therapy protocols) play in the development of osteonecrosis. The planned intervention will therefore encompass these two periods.

Although TOT17 includes an optional randomization for vincristine and dexamethasone duration (49 weeks vs. 101 weeks), the primary endpoint in this study (Reinduction II MRI) occurs prior to that randomization. Thus, the randomization will not impact the primary outcome of the study. Furthermore, review of symptomatic osteonecrosis timing on TOTXVI suggests that the majority of patients develop symptoms prior to this timepoint. For secondary endpoints including CTCAE symptomatic osteonecrosis, we will consider dexamethasone duration as a covariate.

